## **ECG Changes**

A participant who meets either bulleted criteria based on the average of triplicate ECG readings will be withdrawn from the study intervention.

- QTc, QTcB, QTcF >500 msec.
- Change from baseline: QTc >60 msec.

If a clinically significant finding is identified (including, but not limited to, changes from baseline in QTcF after enrollment), the investigator or qualified designee will determine if the participant can continue in the study and if any change in participant management is needed. This review of the ECG printed at the time of collection must be documented. Any new clinically relevant finding should be reported as an AE.

### **Potential Cases of Acute Kidney Injury**

Abnormal values in SCr concurrent with presence or absence of increase in BUN that meet the criteria below, in the absence of other causes of kidney injury, are considered potential cases of acute kidney injury and should be considered important medical events.

An increase of  $\geq 0.3$  mg/dL (or  $\geq 26.5$  µmol/L) in SCr level relative to the participant's own baseline measurement should trigger another assessment of SCr as soon as practically feasible, preferably within 48 hours from awareness.

If the second assessment (after the first observations of  $\geq$ 0.3 mg/dL [or  $\geq$ 26.5  $\mu$ mol/L] in SCr relative to the participant's own baseline measurement) is  $\geq$ 0.4 mg/dL (or  $\geq$ 35.4  $\mu$ mol/L), the participant should be discontinued from the study and adequate, immediate, supportive measures taken to correct apparent acute kidney injury.

Participants should return to the investigator site and be evaluated as soon as possible, preferably within 48 hours from awareness of the second assessment confirming abnormal SCr result. This evaluation should include laboratory tests, detailed history, and physical assessment. In addition to repeating SCr, laboratory tests should include serum BUN, serum creatine kinase, and serum electrolytes (including at a minimum potassium, sodium,

phosphate/phosphorus, and calcium), in addition to urinary dipstick, urine microscopic examination, and urinary indices. All cases confirmed on repeat testing as meeting the laboratory criteria for acute kidney injury, with no other cause(s) of laboratory abnormalities identified, should be considered potential cases of drug-induced kidney injury irrespective of availability of all the results of the investigations performed to determine etiology of the abnormal SCr. If  $\geq$ 2 healthy participants in a given period in PART-1 and 3 and in a treatment arm in PART-2 are noted to have 2 consecutive SCr results of  $\geq$ 0.3 mg/dL (or  $\geq$ 26.5 µmol/L), an assessment of whether the finding may be considered an adverse drug reaction should be undertaken.

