### • Positive COVID-19 test.

If study intervention is definitively discontinued, the participant will not remain in the study for further evaluation. See the SoA for data to be collected at the time of discontinuation of study intervention.

In the event of discontinuation of study intervention, it must be documented on the appropriate CRF/in the medical records whether the participant is discontinuing further receipt of study intervention or also from study procedures, posttreatment study follow-up, and/or future collection of additional information.

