# 7.2. Participant Discontinuation/Withdrawal From the Study

A participant may withdraw from the study at any time at his/her own request. Reasons for discontinuation from the study include the following:

- Refused further follow-up;
- Lost to follow-up;
- Death:
- Study terminated by sponsor;
- Investigator's decision;
- Pregnancy.

At the time of discontinuing from the study, if possible, an early discontinuation visit should be conducted. See the SoA for assessments to be collected at the time of study discontinuation and follow-up and for any further evaluations that need to be completed.

The early discontinuation visit applies only to participants who are enrolled/randomized and then are prematurely withdrawn from the study. Participants should be questioned regarding their reason for withdrawal.

The participant will be permanently discontinued both from the study intervention and from the study at that time.

If a participant withdraws from the study, he/she may request destruction of any remaining samples taken and not tested, and the investigator must document any such requests in the site study records and notify the sponsor accordingly.

If the participant withdraws from the study and also withdraws consent (see Section 7.2.1) for disclosure of future information, no further evaluations should be performed and no additional data should be collected. The sponsor may retain and continue to use any data collected before such withdrawal of consent.

Lack of completion of all or any of the withdrawal/early termination procedures will not be viewed as protocol deviations so long as the participant's safety was preserved.

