### 9.2. Sample Size Determination

A total of up to 78 participants (12 in PART-1: SAD, up to 30 [with 2 cohorts and 3 optional cohorts] in PART-2: MAD, a maximum of 18 in PART-3: Relative Bioavailability/Food Effect cohort,6 in PART-4: metabolism and excretion and up to 12 in PART-5: Supratherapeutic Exposure) are planned to be randomized in this study. Participants who discontinue for reasons other than safety during the study may be replaced at the discretion of the sponsor and Investigator.

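### The serum-creatinine limit that discontinues a participant (0.4 mg/dL), and the later 0.3 mg/dL group rule, are not worded as rises from baseline; read literally, a repeat back at baseline still means discontinuation

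*Protocol*

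**What the plan says.** Protocol Section 7.1, under Potential Cases of Acute Kidney Injury, gives three SCr limits.

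1. **Repeat trigger.** An increase of at least 0.3 mg/dL (26.5 µmol/L) "in SCr level relative to the participant's own baseline measurement should trigger another assessment of SCr as soon as practically feasible". This one is explicitly a change from baseline.
2. **Individual discontinuation.** A bracket recalls the first observation and ends "in SCr relative to the participant's own baseline measurement) is", followed directly by the limit of at least 0.4 mg/dL (35.4 µmol/L). If the second assessment meets it, "the participant should be discontinued from the study and adequate, immediate, supportive measures taken to correct apparent acute kidney injury".
3. **Group rule.** If two or more participants, in a period of PART-1 or PART-3 or in a treatment arm of PART-2, each have two consecutive SCr results of at least 0.3 mg/dL, "an assessment of whether the finding may be considered an adverse drug reaction should be undertaken". No baseline is mentioned.

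The ECG rule just above in Section 7.1 does label its change criterion, "Change from baseline: QTc >60 msec", and keeps it separate from the absolute limit of 500 msec.

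On the consequences, Section 7.1 states: "If study intervention is definitively discontinued, the participant will not remain in the study for further evaluation". Section 7.2 adds: "The participant will be permanently discontinued both from the study intervention and from the study at that time". Section 9.2 restricts replacement: "Participants who discontinue for reasons other than safety during the study may be replaced at the discretion of the sponsor and Investigator".

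**The concern.** The repeat is there to separate a confirmed rise in creatinine from a transient one. In the discontinuation sentence the baseline reference belongs to the first observation, and the bracket closes before the 0.4 mg/dL limit. What is left is an absolute creatinine of 0.4 mg/dL, which cannot do that job: it clears nobody whose repeat is 0.4 mg/dL or higher, including someone fully back at baseline.

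This is an operative stopping rule for individuals in a first-in-human study. Followed as printed, it would remove a participant with a transient rise from both treatment and study. Because the reason is safety, the replacement provision would not cover the loss. Cohorts are small: PART-1 and PART-2 plan about 4 active participants per dose level, and Section 6.6 requires data from at least 3 of them before escalation. Data already collected are kept, so a single loss does not by itself block escalation.

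The group rule has the same gap. Taken literally, it would be met by ordinary creatinine values and could not identify a signal, although it leads only to an assessment.

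**Working it through.** **Inputs.** The three limits are those of Protocol Section 7.1. The dosing schedule is that of Section 4.1, PART-2. The documents give no SCr reference range or baseline value, so baselines *b* of 0.5 to 1.2 mg/dL are an assumption.

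**The plan's own figures.** With 1 mg/dL = 88.4 µmol/L:
- 0.3 × 88.4 = 26.52, printed as 26.5.
- 0.4 × 88.4 = 35.36, printed as 35.4.

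The unit pairs agree, so a unit error does not explain the wording.

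**Example.** Baseline 0.8, first value 1.1, repeat 0.8 mg/dL.
- Repeat trigger: 1.1 − 0.8 = 0.3, so a repeat is required.
- Discontinuation limit as printed: 0.8 ≥ 0.4, met.
- Discontinuation limit as a rise: 0.8 − 0.8 = 0, which is below 0.4, not met.

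**Range.** As printed, the repeat avoids discontinuation only if it is below 0.4 mg/dL. The fall below baseline that this requires is more than (b − 0.4)/b. Read as a rise, the limit is b + 0.4.

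| Assumed baseline (mg/dL) | Fall below baseline needed, as printed | Limit if a rise is meant (mg/dL) |
|---|---|---|
| 0.5 | 0.1/0.5 = 20% | 0.9 |
| 0.6 | 0.2/0.6 = 33% | 1.0 |
| 0.8 | 0.4/0.8 = 50% | 1.2 |
| 1.0 | 0.6/1.0 = 60% | 1.4 |
| 1.2 | 0.8/1.2 = 67% | 1.6 |

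Read literally, a repeat exactly at baseline meets the discontinuation limit whenever b is at least 0.4 mg/dL. Two consecutive results at baseline meet the group limit whenever b is at least 0.3 mg/dL. Read as rises, neither limit is met at any baseline.

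**What one discontinuation costs.** Take a PART-2 participant stopped before the Day 6 dose.
- BID: 9 × 2 + 1 = 19 planned doses; from Day 6 on, 4 × 2 + 1 = 9 are missed.
- TID: 9 × 3 + 1 = 28 planned doses; from Day 6 on, 4 × 3 + 1 = 13 are missed.
- The Day 10 PK is lost under either regimen.

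A PART-1 participant stopped in Period 1 misses Period 2 and any optional Periods 3 and 4.

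**Whether other text cures it.** No other part of the protocol restates either limit. SAP Section 3.5.2 defines the laboratory baseline but does not repeat the SCr rule. Where the protocol means a change elsewhere, it says so: QTc in Sections 7.1 and 8.2.3, and bilirubin in Appendix 6.

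**The case against.** The strongest reply is that this is shorthand no competent reader would misread. The subsection opens by confining itself to abnormal SCr values without another cause. It describes the second assessment as one that confirms an abnormal result, and later requires confirmation on repeat testing. A repeat at the participant's own baseline confirms nothing. The group rule reuses the 0.3/26.5 pair already defined as a rise, and as an absolute value it would be met by almost any adult.

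Other sections also lower the risk. Section 8 has safety issues discussed with the sponsor when deciding whether a participant continues. Section 8.2.4 treats a return to baseline as the end point for repeating abnormal tests. The SCr rule says participants should be discontinued, whereas the ECG rule says they will be withdrawn. If misapplied, it errs toward stopping a healthy volunteer who has no benefit to lose.

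Much of this stands. The intended meaning is recoverable. The discontinuation limit is reached only after a genuine first rise of at least 0.3 mg/dL. The group rule stops nobody. The missed-dose counts describe any discontinuation at that time and do not show that the wording will cause one.

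None of it rewords either limit, however. Section 8 also bars waivers and makes adherence a requirement, so an investigator who sensibly keeps a recovered participant departs from the printed rule, while one who follows it removes that participant needlessly. Section 4.1 allows one to three sites, so the rule could be applied differently between them.

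**Conclusion.** The concern holds. As printed, neither the 0.4 mg/dL discontinuation limit nor the 0.3 mg/dL group limit is expressed as a rise from baseline, and nothing elsewhere corrects them. Once a first rise of at least 0.3 mg/dL has triggered the repeat, the literal rule discontinues anyone whose repeat is 0.4 mg/dL or more. At the assumed baselines that includes every participant whose creatinine has returned to baseline.

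The size of the effect rests on two assumptions: those baselines, and literal application of the rule. The second is not the likeliest behaviour, since context points clearly to a rise. The defect therefore lies in the wording of an operative safety threshold, with limited practical impact and no effect on sample size or planned analyses. It should be corrected because it governs individual stopping in a first-in-human study and the correction is simple.

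**What to change.** Add the baseline reference in both places in Section 7.1.

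1. **Discontinuation limit:** if the second assessment is also increased by at least 0.4 mg/dL (35.4 µmol/L) relative to the participant's own baseline, the participant should be discontinued.
2. **Group rule:** two consecutive SCr results, each increased by at least 0.3 mg/dL (26.5 µmol/L) relative to the participant's own baseline.

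The 0.3 and 0.4 levels can stay. The cost is two phrases in a protocol amendment or clarification letter, with no new data and no change to sample size or analysis.

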# 7.2. Participant Discontinuation/Withdrawal From the Study

A participant may withdraw from the study at any time at his/her own request. Reasons for discontinuation from the study include the following:

- Refused further follow-up;
- Lost to follow-up;
- Death:
- Study terminated by sponsor;
- Investigator's decision;
- Pregnancy.

At the time of discontinuing from the study, if possible, an early discontinuation visit should be conducted. See the SoA for assessments to be collected at the time of study discontinuation and follow-up and for any further evaluations that need to be completed.

The early discontinuation visit applies only to participants who are enrolled/randomized and then are prematurely withdrawn from the study. Participants should be questioned regarding their reason for withdrawal.

The participant will be permanently discontinued both from the study intervention and from the study at that time.

If a participant withdraws from the study, he/she may request destruction of any remaining samples taken and not tested, and the investigator must document any such requests in the site study records and notify the sponsor accordingly.

If the participant withdraws from the study and also withdraws consent (see Section 7.2.1) for disclosure of future information, no further evaluations should be performed and no additional data should be collected. The sponsor may retain and continue to use any data collected before such withdrawal of consent.

Lack of completion of all or any of the withdrawal/early termination procedures will not be viewed as protocol deviations so long as the participant's safety was preserved.

### 7.2.1. Withdrawal of Consent

Participants who request to discontinue receipt of study intervention will remain in the study and must continue to be followed for protocol-specified follow-up procedures. The only exception to this is when a participant specifically withdraws consent for any further contact with him or her or persons previously authorized by the participant to provide this information. Participants should notify the investigator in writing of the decision to withdraw consent from future follow-up, whenever possible. The withdrawal of consent should be explained in detail in the medical records by the investigator, as to whether the withdrawal is only from further receipt of study intervention or also from study procedures and/or posttreatment study follow-up, and entered on the appropriate CRF page. In the event that vital status (whether the participant is alive or dead) is being measured, publicly available information should be used to determine vital status only as appropriately directed in accordance with local law.

### 7.3. Lost to Follow-up

A participant will be considered lost to follow-up if he or she repeatedly fails to return for scheduled visits and is unable to be contacted by the study site.

The following actions must be taken if a participant fails to return to the clinic for/attend a required study visit:

- The site must attempt to contact the participant and reschedule the missed visit as soon as possible and counsel the participant on the importance of maintaining the assigned visit schedule and ascertain whether or not the participant wishes to and/or should continue in the study.
- Before a participant is deemed lost to follow-up, the investigator or designee must make every effort to regain contact with the participant (where possible, 3 telephone calls and, if necessary, a certified letter to the participant's last known mailing address or local equivalent methods). These contact attempts should be documented in the participant's medical record.
- Should the participant continue to be unreachable, he/she will be considered to have withdrawn from the study.

### 8. STUDY ASSESSMENTS AND PROCEDURES

The investigator (or an appropriate delegate at the investigator site) must obtain a signed and dated ICD before performing any study-specific procedures.

Study procedures and their timing are summarized in the SoA. Protocol waivers or exemptions are not allowed.

Safety issues should be discussed with the sponsor immediately upon occurrence or awareness to determine whether the participant should continue or discontinue study intervention.

Adherence to the study design requirements, including those specified in the SoA, is essential and required for study conduct.

All screening evaluations must be completed and reviewed to confirm that potential participants meet all eligibility criteria. The investigator will maintain a screening log to record details of all participants screened and to confirm eligibility or record reasons for screening failure, as applicable.

Participants will be screened within 28 days prior to administration of the study intervention to confirm that they meet the study population criteria for the study. If the time between screening and dosing exceeds 28 days as a result of unexpected delays (eg, delayed drug shipment), then participants do not require rescreening if the laboratory results obtained prior to first dose administration meet eligibility criteria.

A participant who qualified for this protocol but did not enroll from an earlier cohort/group may be used in a subsequent cohort/group without rescreening, provided laboratory results obtained prior to the first dose administration meet eligibility criteria for this study. In addition, other clinical assessments or specimen collections, eg, banked biospecimens, may be used without repeat collection, as appropriate.

Every effort should be made to ensure that protocol-required tests and procedures are completed as described. However, it is anticipated that from time to time there may be circumstances outside the control of the investigator that may make it unfeasible to perform the test. In these cases, the investigator must take all steps necessary to ensure the safety and well-being of the participant. When a protocol-required test cannot be performed, the investigator will document the reason for the missed test and any corrective and preventive actions that he or she has taken to ensure that required processes are adhered to as soon as possible. The study team must be informed of these incidents in a timely manner.

If an IV catheter is utilized for blood sample collections, ECGs and vital sign assessments (pulse rate and BP) should be collected prior to the insertion of the catheter.

For samples being collected and shipped, detailed collection, processing, storage, and shipment instructions and contact information will be provided to the investigator site prior to initiation of the study.

The total blood sampling volume for individual participants in this study may be up to approximately 480 mL, 290 mL, 160 mL, 205 mL and 485 mL in PART-1, PART-2, PART-3, PART-4 and PART-5, respectively. The actual collection times of blood sampling may change. Additional blood samples may be taken for safety assessments at times specified by Pfizer, provided the total volume taken during the study does not exceed 550 mL during any period of 60 consecutive days.

To prepare for study participation, participants will be instructed on the information in the Lifestyle Considerations and Concomitant Therapy sections of the protocol.

## 8.1. Efficacy Assessments

No efficacy assessment is planned in this study.

## 8.2. Safety Assessments

Planned time points for all safety assessments are provided in the SoA. Unscheduled clinical laboratory measurements may be obtained at any time during the study to assess any perceived safety issues.

## 8.2.1. Physical Examinations

A complete physical examination will include, at a minimum, head, ears, eyes, nose, mouth, skin, heart and lung examinations, lymph nodes, and gastrointestinal, musculoskeletal, and neurological systems.

A brief physical examination will include, at a minimum, assessments of general appearance, the respiratory and cardiovascular systems, and participant-reported symptoms.

Physical examinations may be conducted by a physician, trained physician's assistant, or nurse practitioner as acceptable according to local regulation.

Height and weight will also be measured and recorded as per the SoA. For measuring weight, a scale with appropriate range and resolution is used and must be placed on a stable, flat surface. Participants must remove shoes, bulky layers of clothing, and jackets so that only light clothing remains. They must also remove the contents of their pockets and remain still during measurement of weight.

### 8.2.2. Vital Signs

Supine BP will be measured with the participant's arm supported at the level of the heart, and recorded to the nearest mm Hg after approximately 5 minutes of rest. The same arm (preferably the dominant arm) will be used throughout the study. Participants should be instructed not to speak during measurements.

The same properly sized and calibrated BP cuff will be used to measure BP each time. The use of an automated device for measuring BP and pulse rate is acceptable; however, when done manually, pulse rate will be measured in the brachial/radial artery for at least 30 seconds. When the timing of these measurements coincides with a blood collection, BP and pulse rate should be obtained prior to the nominal time of the blood collection.

Additional collection times, or changes to collection times, of BP and pulse rate will be permitted, as necessary, to ensure appropriate collection of safety data.

## 8.2.2.1. Respiratory Rate

Respiratory rate will be measured after approximately 5 minutes of rest in a supine position by observing and counting the respirations of the participant for 30 seconds and multiplying by 2. When BP is to be taken at the same time, respiration measurement will be done during the 5 minutes of rest and before BP measurement.

## 8.2.2.2. Temperature

Temperature will be measured orally. No eating, drinking, or smoking is allowed for 15 minutes prior to the measurement.

### 8.2.3. Electrocardiograms

Standard 12-lead ECGs utilizing limb leads (with a 10 second rhythm strip) should be collected at times specified in the SoA section of this protocol using an ECG machine that automatically calculates the heart rate and measures PR, QT, and QTc intervals and QRS complex. Alternative lead placement methodology using torso leads (eg, Mason-Likar) is not recommended given the potential risk of discrepancies with ECGs acquired using standard limb lead placement. All scheduled ECGs should be performed after the participant has rested quietly for at least 10 minutes in a supine position.

In PART-1 and PART-5, triplicate 12-lead ECGs will be obtained approximately 2 to 4 minutes apart; the average of the triplicate ECG measurements collected before dose administration on Day 1 of each period will serve as each participant's baseline QTc value.

In PART-2, triplicate 12-lead ECGs will be obtained approximately 2 to 4 minutes apart; the average of the triplicate ECG measurements collected at each nominal time point on Day 1 in MAD cohorts will serve as each participant's time-controlled baseline QTc value.

To ensure safety of the participants, a qualified individual at the investigator site will make comparisons to baseline measurements. Additional ECG monitoring will occur if a) the mean value from the triplicate measurements for any postdose QTcF interval is increased by ≥60 msec from the baseline and is >450 msec; or b) an absolute QTcF value is ≥500 msec for any scheduled ECG. If either of these conditions occurs, then a single ECG measurement must be repeated at least hourly until QTcF values from 2 successive ECGs fall below the threshold value that triggered the repeat measurement.

For PART-3 and PART-4 only (when Single ECGs are conducted): To ensure safety of the participants, a qualified individual at the investigator site will make comparisons to baseline measurements. Additional ECG monitoring will occur if a) a postdose QTc interval is increased by ≥60 msec from the baseline and is >450 msec; or b) an absolute QTc value is ≥500 msec for any scheduled ECG. If either of these conditions occurs, then 2 additional ECGs will be collected approximately 2 to 4 minutes apart to confirm the original measurement. If the QTc values from these repeated ECGs remain above the threshold value, then a single ECG must be repeated at least hourly until QTc values from 2 successive ECGs fall below the threshold value that triggered the repeat measurement.

If a) a postdose QTc interval remains  $\ge 60$  msec from the baseline and is  $\ge 450$  msec; or b) an absolute QTc value is  $\ge 500$  msec for any scheduled ECG for greater than 4 hours (or sooner, at the discretion of the investigator); or c) QTc intervals get progressively longer, the participant should undergo continuous ECG monitoring. A cardiologist should be consulted if QTc intervals do not return to less than the criterion listed above after 8 hours of monitoring (or sooner, at the discretion of the investigator).

In some cases, it may be appropriate to repeat abnormal ECGs to rule out improper lead placement as contributing to the ECG abnormality. It is important that leads be placed in the same positions each time in order to achieve precise ECG recordings. If a machine-read QTc value is prolonged, as defined above, repeat measurements may not be necessary if a qualified medical provider's interpretation determines that the QTc values are in the acceptable range.

ECG values of potential clinical concern are listed in Appendix 7.

